7.2 ADVERSE EVENTS—SEVERITY RATING

AEs will be assessed according to CTCAE version 4.0 ([National Cancer Institute, 2009](#)). AEs that do not have a corresponding CTCAE term will be assessed according to their impact on the participant's ability to perform daily activities as listed below.

The severity of each AE should be characterized and then classified into one of five clearly defined categories as follows:

- **Mild (Grade 1):** the AE does not interfere in a significant manner with the subject's normal functioning level—it may be an annoyance
- **Moderate (Grade 2):** the AE produces some impairment of functioning, but is not hazardous to health—it is uncomfortable or an embarrassment
- **Severe (Grade 3):** the AE produces significant impairment of functioning or incapacitation and is a definite hazard to the subject's health
- **Life threatening (Grade 4):** Life threatening or disabling
- **Fatal (Grade 5):** Causes death of the participant

These five categories are based on the Investigator's clinical judgment, which in turn depends on consideration of various factors such as the subject's reports, the Investigator's observations, and the Investigator's prior experience. The severity of the AE should be recorded in the appropriate eCRF. The evaluation of severity is distinguished from the evaluation of "seriousness." A severe event might not meet the criteria for seriousness and a serious event might be evaluated as mild. For example, a subject might have a severe headache that does not require hospitalization and is consequently not serious; or a subject might have a mild myocardial infarction that requires hospitalization and is therefore serious.

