7.4.3 Disease Progression and Death

Disease progression (including progression of hematologic condition and/or organ dysfunction of AL amyloidosis, and death due to disease progression) is generally recorded as part of the efficacy evaluation and should not be reported as a specific AE or SAE. When an AE resulting from disease progression meets the requirements to be considered serious, the SAE verbatim term should be reported as the sign/symptom that best describes the event rather than as “disease progression.” For instance, a subject with pleural effusion presents with shortness of breath. The cause of the shortness of breath is a pleural effusion resulting from disease progression. The event term may be reported as “pleural effusion” instead of disease progression.

Death should not be reported as an SAE, but as a clinical outcome of a specific SAE. The cause of death, reported on a source document such as the Death Certificate or autopsy report, should be used as the event term for the SAE. For example, in a subject with acute heart failure that results in death, the SAE is reported as “acute heart failure” with an outcome of “death.”

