9.2. Adverse Events

Verbatim terms on the OLE Adverse Event eCRFs will be mapped to PT and SOC using MedDRA version 19.0. AEs will be reported and severity will be categorized using the Common Terminology Criteria for Adverse Events (CTCAE, Version 4.03).

AE summaries will use the OLE Safety Population.

All AE summaries will be restricted to treatment-emergent adverse events (TEAEs), which are defined as any AE that newly appears, increases in frequency, or worsens in severity following initiation of study drug and up to 30 days after date of last dose or last study visit, whichever is later. If it cannot be determined whether the AE is treatment emergent due to a partial onset date, then it will be counted as such.

Each AE summary will be displayed by treatment group. Summaries that are displayed by SOC and PT will be ordered by descending order of NEOD001-OLE001 24 mg/kg incidence of SOC and PT within each SOC.

The following listings will be presented by subject, with non-TEAEs flagged:

- All AEs
- Serious adverse events (SAEs) (this is a subset of the AEs where serious is marked as “Yes”)
- CTCAE Grade 3 or higher AEs (this is a subset of AEs where severity is missing or marked as CTCAE Grade 3, 4, or 5)
- Related AEs (this is a subset of the AEs where relationship marked as “Related” or relationship is missing)
- AEs leading to Study Drug Withdrawal (this is a subset of the AEs where Action Taken with Study Treatment is checked as “Drug Discontinued”)
- Fatal AEs (this is a subset of the AEs where outcome is indicated as “Fatal” or the CTCAE grade is 5)
- AEs resulting in any dose change (i.e., interruption, reduction, held, or prolongation)
- AEs assessed by the investigator as infusion-associated (this is a subset of the AEs where infusion-associated AE was reported as "Yes.")
- AEs within one day of any infusion (this is a subset of the AEs where AE onset date was the same day as the date of any infusion)

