9.2.2. Overall Summary of Adverse Events

An overall summary of crude AE incidences will be presented according to [Table 7](#), including the number and percent of subjects with at least one of:

- Any TEAE
- TEAE by maximum CTCAE Grade
- CTCAE Grade ≥ 3 TEAE
- Serious TEAE
- Fatal TEAEs (outcome="Fatal" or severity=CTCAE Grade 5)
- Treatment-related TEAE
- Treatment-related serious TEAE
- Treatment-related TEAE of CTCAE \geq Grade 3
- TEAE leading to infusion interruption

- TEAE leading to dose reduction
- TEAE leading to dose being held
- TEAE leading to prolongation of infusion time (>2.5 hours)
- Infusion associated TEAE as determined by the Investigator
- TEAE leading to study drug withdrawal

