9.2.4. Severity of Adverse Events

The crude and cumulative incidences of TEAEs by maximum severity will be summarized. At each level of subject summarization, a subject is classified according to the highest severity if the subject reported 1 or more events. AEs with missing severity (CTCAE grade) will be considered Grade 3 (severe) for these summaries. The following summaries will be presented:

- Subject incidence of TEAEs by MedDRA SOC, PT, and highest severity (CTCAE grade)
- Subject incidence of CTCAE Grade 3 or higher TEAEs by MedDRA SOC and PT.

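### SAP 9.2.4 tabulates an adverse event with no CTCAE grade as Grade 3 even when its outcome is fatal, so a subject counted as a death elsewhere can appear below Grade 5 in the severity tables

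*SAP*

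**What the plan says.** SAP 9.2.4 governs the summaries of treatment-emergent adverse events (TEAEs) by maximum severity. Its missing-grade rule reads: "AEs with missing severity (CTCAE grade) will be considered Grade 3 (severe) for these summaries". Within each level of summarization, "a subject is classified according to the highest severity if the subject reported 1 or more events".

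Fatal events are identified differently. For the fatal listing, SAP 9.2 says "this is a subset of the AEs where outcome is indicated as “Fatal” or the CTCAE grade is 5". The overall summary in SAP 9.2.2 defines its fatal row in the same way, and that summary also contains "TEAE by maximum CTCAE Grade". SAP 9.2.7 adds a table of fatal TEAEs by system organ class and preferred term.

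Protocol 7.2 describes a Grade 5 event in these words: "Causes death of the participant". Neither document contains a rule that derives Grade 5 from a fatal outcome.

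**The concern.** Treating a missing grade as Grade 3 is a cautious default for a non-fatal event, because the true grade is unknown and the rule leans towards severe. For an event with a fatal outcome the default works the other way. The outcome field already shows that the event belongs in the worst class of the protocol's scale, and the rule replaces that with a grade two steps lower.

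Frequency and severity of adverse events are part of the primary endpoint (Protocol 3.2.1, SAP 2.3.1). If the rule is triggered, the report can show one fatal subject under a preferred term in the 9.2.7 table and no Grade 5 subject under the same term in the 9.2.4 table. A reader could not tell which was right. The error also runs in one direction: it can lower the Grade 5 count but never raise it.

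**Working it through.** The plan gives no figure to reproduce, so the check applies its rules to test records.

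**Rules used**
- Missing grade becomes Grade 3, and each subject is placed at the highest grade (SAP 9.2.4).
- An event is fatal if its outcome is fatal or its grade is 5 (SAP 9.2, 9.2.2).
- An event that causes death is Grade 5 (Protocol 7.2).

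**Six hypothetical subjects**

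| Subject | TEAEs | Counted as fatal | Highest grade, 9.2.4 as written | Highest grade if missing grade + fatal = 5 |
|---|---|---|---|---|
| A | Grade 5, fatal | yes | 5 | 5 |
| B | no grade, fatal | yes | 3 | 5 |
| C | Grade 4, fatal; Grade 2, non-fatal | yes | 4 | 4 |
| D | no grade, fatal; Grade 4, non-fatal | yes | 4 | 5 |
| E | Grade 3, non-fatal | no | 3 | 3 |
| F | no grade, non-fatal | no | 3 | 3 |

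**Counts**
- Fatal: 4 (A, B, C, D) throughout.
- Grade 5: 1 (A) as written, and 3 (A, B, D) with the amended rule.
- Grade 3 or higher: 6 as written and 6 with the amended rule.
- The one remaining difference after the amendment (3 against 4) is subject C, whose fatal event has a recorded grade of 4.

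**Direction.** Every Grade 5 subject meets the fatal definition, but not every fatal subject is Grade 5. The Grade 5 count can therefore equal the fatal count or fall below it, and can never exceed it.

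**Level of summarization.** Subject D appears at Grade 4 overall only because of a second event. If the two events fall under different preferred terms, the row for the fatal term shows D at Grade 3.

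**The 9.2.2 summary.** The wording of the Grade 3 rule ties it to the 9.2.4 tables, and 9.2.2 states no missing-grade rule. If ungraded events are left ungraded there, the Grade 5 count is still 1 against 4 fatal, and Grade 3 or higher falls from 6 to 4 because B and F drop out. The SAP does not say which treatment applies.

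**Size per subject.** On the planned enrolment of about 70 (Protocol 3.3), one subject is 1/70 = 1.4%. The parent study enrolled 69 (Protocol 1.3.2), and 1/69 is also 1.4%. If fewer subjects enter the extension, the share is 1/N and correspondingly larger.

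**The case against.** The strongest reply is that no death is lost. Fatal events are found by outcome or grade, and they have their own row, table and listing. Cumulative incidence of deaths is also summarized. The Grade 3 or higher listing keeps ungraded events by design: "this is a subset of AEs where severity is missing or marked as CTCAE Grade 3, 4, or 5". No inferential safety comparison is planned unless otherwise specified (SAP 9). All of this stands, and it limits the point to the split by grade.

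The second reply is that the trigger is a data defect that the protocol already works against. Severity must be assigned to every event (Protocol 7.1), the investigator verifies the case report forms (9.1), and the monitor checks completeness and consistency (9.3). This also stands, and there may be no affected record. It does not rescue the rule, however. The SAP wrote a rule for missing grades, and for a fatal event that rule gives the wrong answer.

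A reader might infer more than the documents support:
- *That the 9.2.4 rule itself sets grades in the 9.2.2 summary.* It is confined to the 9.2.4 tables. A mismatch in 9.2.2 arises only because nothing there maps a fatal outcome to Grade 5.
- *That the SAP expects outcome and grade to disagree.* Defining fatal by either field is also ordinary defensive programming.
- *That the protocol's reporting convention creates the mismatch.* Protocol 7.4.3 says "Death should not be reported as an SAE, but as a clinical outcome of a specific SAE". The event that carries that outcome is exactly the one Protocol 7.2 grades 5, so the convention does not by itself separate the two fields.
- *That every fatal-outcome event should be reset to Grade 5 by program.* Protocol 7.2 leaves grading to the investigator's judgment. Overwriting a recorded Grade 3 or 4 is debatable, and a data query is the route the protocol's own controls point to.

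**Conclusion.** The point holds in a narrow form. For a fatal TEAE with no grade, SAP 9.2.4 assigns a grade that conflicts with Protocol 7.2 and with the SAP's own fatal outputs. The visible effect requires at least one such record in a subject with no other Grade 5 TEAE at that level of summarization. Each affected subject then moves from Grade 5 to Grade 3, or to Grade 4 where another event sets the maximum, which is about 1.4 percentage points on 70.

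The documents do not say how many fatal or ungraded events there are, so no proportion of missed Grade 5 subjects can be given. A reader might infer that deaths are under-reported or that the rate of severe events is too low. Neither follows: death counts and the Grade 3 or higher counts in 9.2.4 stay the same. This is a minor correction to a descriptive table, worth making because it is cheap and removes an avoidable contradiction between outputs.

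**What to change.** Replace the missing-grade sentence in SAP 9.2.4 with a two-part rule: an event with no CTCAE grade and a fatal outcome is analysed as Grade 5, and any other event with no grade is analysed as Grade 3. State in 9.2.2 that the same rule applies to the maximum-grade rows.

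Query before database lock any fatal-outcome event with a recorded grade below 5. If some remain, keep the recorded grade and footnote the tables, so that a difference between the Grade 5 and fatal counts is explained.

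The cost is one or two SAP sentences, one line of derivation code and a short data query. No new data are needed.

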9.2.5. Relationship to Study Drug as Assessed by Investigator

The crude and cumulative incidences of TEAEs by strongest relationship to study drug (Related/Not Related) will be summarized. At each level of subject summarization, a subject is classified according to the closest relationship to study drug if the subject reported 1 or more events. AEs with a missing relationship will be considered related for this summary. The following summaries will be presented:

- Subject incidence of related TEAEs by MedDRA SOC and PT
- Subject incidence of related CTCAE Grade 3 or higher TEAEs by MedDRA SOC and PT

9.2.6. Adverse Events Leading to Dosing Changes

The crude and cumulative incidences of TEAEs leading to dosing changes will be summarized. The following summaries will be presented:

- Subject incidence of TEAEs leading to infusion interruption by MedDRA SOC and PT. This is a subset of the AEs where Action Taken with Study Treatment is checked as “Dose Interrupted” is checked.

- Subject incidence of TEAEs leading to dose reduction by MedDRA SOC and PT. This is a subset of the AEs where Action Taken with Study Treatment is checked as “Dose Reduced” is checked.
- Subject incidence of TEAEs leading to dose held by MedDRA SOC and PT. This is a subset of the AEs where Action Taken with Study Treatment is checked as “Dose Held” is checked.
- Subject incidence of TEAEs leading to prolongation of infusion time (>2.5 hours) by MedDRA SOC and PT.

9.2.7. Serious Adverse Events and Deaths

The crude incidences of serious TEAEs will be summarized. The incidence of fatal TEAEs will be summarized separately. In addition, the cumulative incidences of serious TEAEs and deaths will be summarized. The following summaries will be presented:

- Subject incidence of serious TEAEs by MedDRA SOC and PT
- Subject incidence of serious related TEAEs by MedDRA SOC and PT
- Subject incidence of fatal TEAEs by MedDRA SOC and PT

9.2.8. Adverse Events Leading to Study Drug Withdrawal

AEs leading to study drug withdrawal are those AEs where Action Taken with Study Treatment is checked as “Drug Discontinued”. The crude and cumulative incidences of AEs leading to study drug withdrawal will be summarized. The following summaries will be presented:

- Subject incidence of TEAEs leading to study drug withdrawal by MedDRA SOC and PT

9.2.9. Other Adverse Events: Infusion Reactions

The crude incidence of infusion associated TEAEs by MedDRA SOC and PT will be summarized. This is a subset of the AEs where the question “Was the event an infusion-associated adverse event?” is checked “Yes”. In addition, the cumulative incidences of TEAEs will be summarized.

If applicable, the crude incidence anaphylactic reaction, defined as the broad algorithmic standardized MedDRA query (SMQ) of “Anaphylactic reaction”, defined in [Appendix 5](#), will be summarized.

In order to explore the temporal relationship of TEAEs that may be associated with the infusion, the crude incidence of all TEAE occurring within 1 day (AE start date – infusion date + 1 = 1) of an infusion will be summarized.

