1 INTRODUCTION

1.1 LIGHT CHAIN (AL) AMYLOIDOSIS

Systemic amyloidoses are a complex group of diseases caused by tissue deposition of misfolded proteins that result in progressive organ damage. The most common type, light chain (AL) amyloidosis or primary systemic amyloidosis, involves a hematologic disorder caused by clonal plasma cells that produce misfolded immunoglobulin light chains. Overproduction of misfolded light chains by plasma cells results in both soluble, aggregated forms of light chains and insoluble, fibrillar deposits of abnormal AL protein (amyloid), in the tissues and organs of individuals with AL amyloidosis. Clinical features of AL amyloidosis include a constellation of symptoms and organ dysfunction including cardiac, renal, and hepatic dysfunction, gastrointestinal involvement, neuropathy and macroglossia. The mechanisms by which amyloidogenic immunoglobulin light chains result in organ dysfunction are not well characterized; however, it is hypothesized that both amyloid deposits and prefibrillar aggregates may contribute to cytotoxic effects on organs observed in patients with AL amyloidosis.

AL amyloidosis is a rare disorder. Although the exact incidence of AL amyloidosis in the United States (US) is unknown, a weighted average from 5 sources ([Kyle et al, 1992](#); [Simms et al, 1994](#); [Kyle et al, 2002](#); [Kyle et al, 2006](#); [Junicon Study](#)) estimates the incidence to be 7.6 new cases per million population per year, which is approximately 2300 new cases per year.

Approximately, two thirds of AL amyloidosis patients present with one or two major organ systems involved (e.g., cardiac, renal, gastrointestinal tract, hepatic, autonomic nervous system, peripheral nervous system, soft tissues) while a third of patients present with more than two systems involved ([Kyle et al, 1992](#)). AL amyloidosis is most commonly associated with cardiac and/or renal dysfunction, with overt restrictive cardiomyopathy observed in approximately 50% of all cases, and subclinical cardiac involvement detected in almost every case at autopsy or on endomyocardial biopsy ([Falk and Dubrey, 2010](#)).

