1.3.2 Clinical Safety

The safety and tolerability of NEOD001 have been investigated in the Phase 1/2 study (Study NEOD001-001) in the US, and are being investigated in the following ongoing global studies:

- Phase 1/2 open-label extension study (Study NEOD001-OLE001)
- Phase 2b study (Study NEOD001-201)
- Phase 3 study (Study NEOD001-CL002)

Study NEOD001-001 was a Phase 1/2 open-label, dose escalation study of the IV administration of single-agent NEOD001 in subjects with AL amyloidosis, which enrolled 27 subjects in the Escalation Phase in 7 cohorts (evaluating dose levels from 0.5 mg/kg to 24.0 mg/kg) and enrolled an additional 42 subjects in the Expansion Phase. The most frequently reported treatment-emergent adverse events (TEAEs) overall in Study NEOD001-001 (occurring in $\geq 10\%$ of subjects [N=69], regardless of relationship to NEOD001) were fatigue, nausea, upper respiratory tract infection, diarrhea, anemia, blood creatinine increased, dizziness, constipation, cough, headache, edema peripheral, vomiting, pain in extremity, back pain, dyspnea, edema, muscle spasms, rash, and urinary tract infection (Gertz et al, 2016). No confirmed anti-NEOD001 antibodies were detected. No dose-limiting toxicities (DLTs) or related serious adverse events (SAEs) were reported.

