APPENDIX 5. ANAPHYLACTIC REACTION SMQ

An Adverse Event or group of Adverse Events occurring on the same day should be flagged as Anaphylactic Reaction per SMQ if the AE(s) meets one or more of the following criteria:

- Any term from group A
- Any two terms, with one from group B and one from group C
- Any two terms, with one from group D and one from either group B or group C

Group A Terms	
Preferred Term	Preferred Term Code
Anaphylactic reaction	10002198
Anaphylactic shock	10002199
Anaphylactic transfusion reaction	10067113
Anaphylactoid reaction	10002216
Anaphylactoid shock	10063119
Circulatory collapse	10009192
Dialysis membrane reaction	10076665
Kounis syndrome	10069167
Shock	10040560
Shock symptom	10040581
Type I hypersensitivity	10045240

Group B Terms	
Preferred Term	Preferred Term Code
Acute respiratory failure	10001053
Asthma	10003553
Bronchial oedema	10056695
Bronchospasm	10006482
Cardio-respiratory distress	10049874
Chest discomfort	10008469
Choking	10008589
Choking sensation	10008590

Group B Terms	
Preferred Term	Preferred Term Code
Circumoral oedema	10052250
Cough	10011224
Cyanosis	10011703
Dyspnoea	10013968
Hyperventilation	10020910
Irregular breathing	10076213
Laryngeal dyspnoea	10052390
Laryngeal oedema	10023845
Laryngospasm	10023891
Laryngotracheal oedema	10023893
Mouth swelling	10075203
Nasal obstruction	10028748
Oedema mouth	10030110
Oropharyngeal oedema	10078783
Oropharyngeal spasm	10031111
Oropharyngeal swelling	10031118
Pharyngeal oedema	10034829
Respiratory arrest	10038669
Respiratory distress	10038687
Respiratory failure	10038695
Reversible airways obstruction	10062109
Sensation of foreign body	10061549
Sneezing	10041232
Stridor	10042241
Swollen tongue	10042727
Tachypnoea	10043089
Throat tightness	10043528
Tongue oedema	10043967
Tracheal obstruction	10044291

Group B Terms	
Preferred Term	Preferred Term Code
Tracheal oedema	10044296
Upper airway obstruction	10067775
Wheezing	10047924

Group C Terms	
Preferred Term	Preferred Term Code
Allergic oedema	10060934
Angioedema	10002424
Erythema	10015150
Eye oedema	10052139
Eye pruritus	10052140
Eye swelling	10015967
Eyelid oedema	10015993
Face oedema	10016029
Flushing	10016825
Generalised erythema	10051576
Injection site urticaria	10022107
Lip oedema	10024558
Lip swelling	10024570
Nodular rash	10075807
Ocular hyperaemia	10030041
Oedema	10030095
Periorbital oedema	10034545
Pruritus	10037087
Pruritus allergic	10063438
Pruritus generalised	10052576
Rash	10037844
Rash erythematous	10037855

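### The anaphylaxis summary under Infusion Reactions is not tied to any infusion date, so symptoms of one cardiac episode weeks after a dose could be counted as anaphylactic reaction

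*SAP*

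**What the plan says.** SAP 9.2.9 plans three things under the heading Infusion Reactions:

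- Treatment-emergent events that the Investigator marked as infusion-associated, by system organ class and preferred term.
- Where applicable, "the crude incidence anaphylactic reaction, defined as the broad algorithmic standardized MedDRA query (SMQ) of" that name.
- All treatment-emergent events starting on an infusion day, by the rule AE start date minus infusion date plus 1 equals 1.

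The query itself is set out in SAP Appendix 5: "An Adverse Event or group of Adverse Events occurring on the same day should be flagged as Anaphylactic Reaction per SMQ" when one of three criteria is met. One Group A term is enough by itself. The second criterion is a B and C combination, worded "Any two terms, with one from group B and one from group C". The third pairs a Group D term with a term from B or C.

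Group A includes Shock and Circulatory collapse. Group B includes Dyspnoea and Cough, Group C includes Oedema and Rash, and Group D includes Hypotension.

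SAP 9.2 restricts all AE summaries to treatment-emergent events, from the start of study drug to the later of 30 days after the last dose and the last study visit. It also plans listings of infusion-associated events and of events on an infusion day.

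**The concern.** The row will be read as infusion-related anaphylaxis because of where it stands, but the rule behind it looks only at whether terms coincide with each other. It uses no infusion date, no infusion-associated flag and no relatedness.

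This matters in a disease with much cardiac involvement. Protocol 1.1 describes AL amyloidosis "with overt restrictive cardiomyopathy observed in approximately 50% of all cases". Protocol 1.3.2 names, among events seen in at least 10% of the 69 parent-study subjects, "cough, headache, edema peripheral, vomiting, pain in extremity, back pain, dyspnea, edema, muscle spasms, rash, and urinary tract infection". Breathlessness with oedema, or hypotension with breathlessness, can be one cardiac event. Recorded as separate terms on one day, it satisfies Appendix 5.

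Safety is the primary objective, there is no control arm to show a background rate, and SAP 8 and 11 drop the efficacy tables, so the safety tables are the study's main summary output. In about 70 subjects, one or two disease-related hits would change how the row reads.

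**Working it through.** The plan states no expected rate for this query, so there is no figure to reproduce. The check has four parts.

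**1. Which combinations qualify.** Counting the terms printed in Appendix 5 gives B = 40, C = 29 and D = 8 (the D list may be cut off in the text available, so 8 is a minimum).

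- All unordered pairs of the 77 terms: 77 × 76 / 2 = 2926.
- Qualifying pairs: 40 × 29 + 8 × (40 + 29) = 1160 + 552 = 1712, or 58.5%.
- Same-group pairs, which do not qualify: 2926 − 1712 = 1214, or 41.5%. Dyspnoea with Cough is one of these.
- Pairs that fit a cardiac episode and do qualify: Dyspnoea or Cough with Oedema (B + C), Hypotension with Dyspnoea (D + B), Hypotension with Oedema (D + C).

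**2. How much of the window is infusion time.** Protocol 6.1.2 gives 36 infusions, one every 28 days. Assume a full course exactly on schedule and a window closing 30 days after the last dose.

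- First to last infusion: 35 × 28 + 1 = 981 days. Adding 30 gives 1011 days.
- Infusion days: 36 / 1011 = 3.6%. The other 96.4% of days are equally eligible under Appendix 5.
- Infusion day or next day: 72 / 1011 = 7.1%.

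These are shares of calendar time. They do not say how many hits will occur.

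**3. How many hits.** The documents give no rate of same-day co-occurrence. Let f be the assumed share of 70 subjects (Protocol 3.3) with at least one qualifying hit away from an infusion. The expected count is 70f, and the chance of at least one is 1 − (1 − f)^70.

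| f (assumed) | Expected subjects flagged | Chance of at least one |
|---|---|---|
| 1% | 0.7 | 51% |
| 2% | 1.4 | 76% |
| 5% | 3.5 | 97% |
| 10% | 7.0 | 99.9% |

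The other extreme is two symptoms that arise independently, each in a share p of subjects, with onset days random over the window. The expected number of coincidences is 70 × p² / 1011, which is 0.0007, 0.003 and 0.006 for p = 10%, 20% and 30%. Chance coincidence is therefore negligible. The issue depends on symptoms of one episode being recorded together.

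**4. What same day means.** Appendix 5 does not say whether it means onset or presence. If presence, chronic oedema could pair with a cough that begins months later. The partial-date rule in SAP 4.3 can also create same-day pairs, because it moves an onset with a missing day to the first of the month, or to a reference date such as the first infusion.

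**The case against.** The strongest reply is that a broad standardised query is meant to be sensitive, that its rules are printed in full, and that the row does not stand alone. A real infusion-day reaction would appear in the infusion-day summary and listing, and in the infusion-associated ones if the Investigator marked it. With about 70 subjects, each hit can be checked by hand. This stands as mitigation. It also answers the inference that this is the only place where a true case would show, or that one could be lost: the documents do not support that. But neither companion summary is crossed with the query, so the anaphylaxis count itself remains unseparated.

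The reply also limits the mechanism. Protocol 7.4.3 generally keeps disease progression out of AE reporting, and its examples reduce an episode to one term, pleural effusion or acute heart failure. Neither is in the printed groups. Peripheral oedema, listed separately in Protocol 1.3.2, is not a printed Group C term. The 50% cardiomyopathy figure describes the disease at large, not entrants who passed eligibility after at least nine months of treatment. These points make hits less certain. They do not exclude them, because the same section has serious events from progression reported under the sign or symptom that best describes them.

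**Conclusion.** The point holds: as written, the anaphylaxis row counts qualifying terms on any day of the treatment-emergent window, so disease symptoms far from a dose could be tabulated under Infusion Reactions.

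Three stronger readings are tempting and are not supported:

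- **That any same-day symptom pair is flagged.** Only B + C or D + (B or C) pairs, or a single Group A term, qualify.
- **That heart-failure symptoms would be reported as reactions to NEOD001.** The SAP attaches no causal meaning to a flag, the summary is conditional, and the outcome depends on how an episode is coded. The right word is could.
- **That several false hits can be predicted.** Protocol 1.3.2 gives each symptom's frequency separately and says nothing about co-occurrence. The range of 0.7 to 7.0 subjects rests wholly on the assumed 1% to 10%, and independent onsets would give under 0.01.

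The 3.6% figure assumes a full 36-infusion course on schedule.

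**What to change.** In SAP 9.2.9 and Appendix 5:

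1. Define same day as same onset date.
2. Keep the total row for the query and split it into (a) hits with onset on an infusion day, by the rule already in 9.2.9, and (b) hits at any other time. Show infusion day or next day as a supplementary window, so that the section keeps one main rule.
3. List every hit with its terms, onset date (marked if imputed), days since the last infusion and the Investigator's infusion-associated flag.

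Hours since the end of infusion are not proposed, because the AE attributes required in Protocol 7.1 include onset and resolution dates but no onset time.

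The cost is small: a date comparison on data already collected, extra rows and one listing. The downside is that a delayed reaction would fall in row (b). It stays visible there, in the total and in the listing, so no hit is removed.
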